APPENDIX 1. PROGRAMMING CONVENTIONS FOR OUTPUTS

OUTPUT FILE NAMING CONVENTIONS

File names should only consist of lowercase letters, digits (0 to 9) and hyphens. A period should only be used to indicate a separator between the file name and the extension. No spaces, other special characters or punctuation marks are permitted.

The program, program log and output file name should reflect the type of the statistical output. The output files will contain the output number in addition. If this is not possible, then the output name should be at least as descriptive as possible. A prefix can be used to distinguish between a Table, Listing and Figure document ('t' for table, 'l' for listing and 'f' for figure). If there is only 1 digit in the number of the table, listing or figure in the place where 2 digits are possible, a leading zero should be added in the file name to make sorting consistent with the sequence (e.g. t-14-3-01-1.RTF)

As far as possible, output files should be in RTF and PDF format.

The outputs will be provided in pdf format.

PAPER SIZE, ORIENTATION AND MARGINS

The size of paper will be Letter.

The page orientation should preferably be landscape, but portrait is also permitted.

Margins should provide at least 1 inch (2.54 centimeters) of white space all around the page, regardless of the paper size.

The number of columns per page (linesize) should be 134 for Letter.

The number of rows per page (pagesize) should be 40 for Letter.

FONTS

The font type 'Courier New' should be used as a default for tables and listings, with a font size of 8. The font color should be black. No bolding, underlining italics or subscripting should be permitted. Try to avoid using super-scripts, unless absolutely necessary. Single spacing should be used for all text.

Figures should have a default font of "Times Roman", "Helvetica", or "Courier New".

This can be achieved by using the following options in SAS:

```
goptions
gunit = pct
cback = white
colors = (black)
hby = 2.4
ftext = "TimesRoman"
htext = 2.5;
```

Document: K:\AAA\Ga-PSMA-R2\VYA27826\ Biostatistics\Documentation\SAP\v2.0\Ga-PSMA-R2-SAP_v2.0
Author: [Redacted] Version Number: 2.0

Version Date: 29JUN2020

Template No.: CS_TP_BS016 Revision 5

Reference: CS_WI_BS005

Effective Date: 01Apr2018

HEADER INFORMATION

Headers should be defined as follows:

- The header should be placed at the top of the page (same place on each page) regardless of the size or orientation of the table or listing
- The customer name and protocol number should appear in row 1, left-aligned
- The output identification number should appear in row 2, left-aligned
- The output title should start in row 2 after output identification number separated by a double dot, left-aligned
- The output population should appear in row 2 after output title separated by a dash, left-aligned. The population should not be spelled out in full, e.g. FAS in preference to Full analysis set.
- Row 3 should be a continuous row of underscores ('_') (the number of underscores should equal the linesize)
- Row 4 should be a blank line
- Mixed case should be used for titles
- The output titles should be designed so that they are arranged consistently through all outputs. For example, content (e.g. Vital Signs) followed by metric (e.g. Change from Baseline) e.g. Vital Signs – Change from Baseline.
- Titles should not contain quotation marks or footnote references
- The column headings should be underlined with a row of underscores ('_')
- Column headings spanning more than one column should be underlined and have underscores on either side of the title and should be centered
- Column headings containing numbers should be centered
- Column headings should be in sentence case
- In general, the population count should appear in the column header in the form "(N=XXX)"
- "Statistic" should be the column header over n, Mean, SE, n (%) etc.
- As a rule, all columns should have column headings.

TABLE AND LISTING OUTPUT CONVENTIONS

General:

- The first row in the body of the table or listing should be blank
- The left-hand column should start in column 1. No indenting or centering of the output should occur.
- Rounding should be done with the SAS function ROUND, if no further specification.
- Numbers in tables should be rounded, not truncated, if no further specification.
- Alphanumeric output should be left aligned.
- Numbers should be decimal point aligned.
- Whole numbers should be right aligned.
- Text values should be left aligned.
- The first letter of a text entry should be capitalized
- Listings of adverse events, concomitant medications, medical histories etc. should be sorted in chronological order, with earliest adverse event, medication or history coming first.
- The study drug should appear first in tables with treatments as columns
- In general, only present totals (across treatment groups) at baseline/randomization, and do not present them post randomization.

Document:	K:\AAA\Ga-PSMA-R2\VYA27826\ Biostatistics\Documentation\SAP\v2.0\Ga-PSMA-R2-SAP_v2.0
Author:	 Version Number: 2.0

Version Date: 29JUN2020

Template No.: CS_TP_BS016 Revision 5
 Effective Date: 01Apr2018

Reference: CS_WI_BS005

- If possible, include 100% frequencies in the table shell, so that it is clear what the denominator is for percentage calculations.
- All listing outputs should be sorted (preferably by Treatment, Site Number and Patient Number).
- Do not use superscripts and subscripts
- The width of the entire output should match the linesize

Univariate Statistics:

- Statistics should be presented in the same order across tables (i.e., n, Mean, Std Dev, Median, Q1, Q3, Minimum, Maximum or n, gMean, gCV, Mean, CV, Std Dev, Median, Minimum, Maximum)
- Table statistics should line up under the N part of the (N=XXX) in the table header. All decimal points should line up. If the minimum and maximum are output on one line as Minimum, Maximum then the comma should line up with the decimal point.
- If the original data has N decimal places, then the summary statistics should have the following decimal places:
 - Minimum and maximum: N
 - Mean, gMean, Q1, Q3, median, gCV% and CV%: N + 1
 - Std Dev: N + 2

Frequencies and percentages (n and %):

- Percent values should be reported inside parentheses, with one space between the count and the left parenthesis of the percentage. Parentheses should be justified to accept a maximum of 100.0 as a value and padded with blank space if the percent is less than 100.0. An example is given below:

```

              77 (100.0%)
              50 (64.9%)
              0 (0.0%)
      
```
- Percentages will be reported to one decimal place, except percentages <100.0% but >99.9% will be presented as '>99.9%' (e.g., 99.99% is presented as >99.9%); and percentages < 0.1% will be presented as '<0.1%' (e.g., 0.08% is presented as <0.1%). Rounding will be applied after the <0.1% and >99.9% rule.

```

      E.g. (<0.1%)
      (6.8%)
      (>99.9%)
      
```
- Percentages may be reported to 0 decimal places as appropriate (for example, where the denominator is relatively small).
- Where counts are zero, percentages of 0.0% should appear in the output.

Confidence Intervals:

- As a rule, confidence intervals are output to one place more than the raw data (except for the primary analysis where we compare against a margin with 3 decimal places), and standard deviations and standard errors to two places more than the raw data
- Confidence intervals should be justified so that parentheses displayed on consecutive lines of a table "line up".
- Boundary values of confidence intervals should be separated by a semi-colon.
- Boundary values should be padded as necessary to accept negative values and to allow alignment of the decimal place.
- An example is given below:

```

              (-0.12; -0.10)
              (9.54; 12.91)
      
```

Document: K:\AAA\Ga-PSMA-R2\VYA27826\Biostatistics\Documentation\SAP\v2.0\Ga-PSMA-R2-SAP_v2.0
 Author:  Version Number: 2.0

Version Date: 29JUN2020

Template No.: CS_TP_BS016 Revision 5
 Effective Date: 01Apr2018

Reference: CS_WI_BS005

P-values:

- P-values should be reported to four decimal places, Rounding will be applied after the <0.0001 and >0.9999 rule

Ratios:

- Ratios should be reported to one more decimal place than the original data.

Spacing:

- There must be a minimum of 1 blank space between columns (preferably 2)

Denominators:

- If a different count other than the population count is used for a denominator (within the table) to calculate percentages, there should be a row in the table that identifies that number "n".
- Alternatively, a footnote should be included in each table with percentages to indicate the denominator for percentages.

Missing values

- A "0" should be used to indicate a zero frequency.
- A blank will be used to indicate missing data in an end-of-text table or patient listing.

FIGURE OUTPUT CONVENTIONS

- Figures will be provided in RTF and PDF files using the SAS Output Delivery System (ODS) as generated by SAS.
- The image should be clear and of high quality when viewed in the Word document, and when printed.
- In general, boxes around the figures should be used.
- Boxplots will display whiskers extending from P10 to first quartile and from 3rd quartile to P90.

FOOTNOTE INFORMATION

Footers should be defined as follows:

- A continuous line of underscores (_) will follow the body of the table or listing prior to any footnotes at the bottom of the page
- Table footnotes should be defined using compute statements in the proc report, and should appear directly after the body of the table
- The program path and name and version number (if applicable) should appear as footnote 1 at the bottom of the page
- The date/time stamp should appear as footnote 2 at the bottom of the page
- Footnotes should be left-aligned.
- Footnotes should be in sentence case.
- Only "typewriter" symbols are permitted – e.g. "*" , "\$" , "#" , "@" , "&" and "–".

Document: K:\AAA\Ga-PSMA-R2\VYA27826\ Biostatistics\Documentation\SAP\v2.0\Ga-PSMA-R2-SAP_v2.0
 Author: [Redacted] Version Number: 2.0
 Version Date: 29JUN2020
 Template No.: CS_TP_BS016 Revision 5 Reference: CS_WI_BS005
 Effective Date: 01Apr2018

Statistical Analysis Plan

- The choice of footnote symbols should be consistent. E.g. if you have the footnote “# indicates last observation carried forward” for one table, the same symbol and footnote should indicate LOCF for all tables.
- If text wraps across more than one line (for a note), the first letter for all lines of text after the first one will be indented to align beneath the first letter of the text in the first line.
- The page identification in the format Page X of Y (where Y is the total number of pages for the output) should appear in the footer, right aligned.

Ordering of footnotes should be as follows:

- 1.) Source data listing reference, if necessary
 - 2.) Abbreviations and definitions
 - 3.) Formulae
 - 4.) P-value significance footnote
 - 5.) Symbols
 - 6.) Specific notes
- Common notes from table to table should appear in the same order.

The symbols should appear in the same order as what they are defined in the table or listing, from left to right.

DATES & TIMES

Depending on data available, dates and times will take the form yyyy-mm-ddThh:mm:ss.

SPELLING FORMAT

English US.

PRESENTATION OF POPULATION GROUPS

For outputs, population groups will be represented as follows and in that order:

Population Group	For Tables, Listings and Graphs
PCa-BR	PCa-BR
mPCa	mPCa
PCa-BR + mPCa	Overall

PRESENTATION OF VISITS

For outputs, visits will be represented as follows and in that order:

Document: K:\AAA\Ga-PSMA-R2\VYA27826\ Biostatistics\Documentation\SAP\v2.0\Ga-PSMA-R2-SAP_v2.0
 Author: [Redacted] Version Number: 2.0
 Version Date: 29JUN2020
 Template No.: CS_TP_BS016 Revision 5 Reference: CS_WI_BS005
 Effective Date: 01Apr2018

Statistical Analysis Plan

Long Name (default)	Short Name
Screening	Screening
Baseline (Day 1)	D1
Day 7	D7
Day 28	D28

LISTINGS

All listings will be ordered by the following (unless otherwise indicated in the template):

- o Population group
- o center-patient ID,
- o date (where applicable)

Document: K:\AAA\Ga-PSMA-R2\VYA27826\ Biostatistics\Documentation\SAP\v2.0\Ga-PSMA-R2-SAP_v2.0
 Author: [REDACTED] Version Number: 2.0

Version Date: 29JUN2020

Template No.: CS_TP_BS016 Revision 5
 Effective Date: 01Apr2018

Reference: CS_WI_BS005

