techniques. Tumor uptake will be evaluated by SUV. SUV _{mean} and SUV _{max} will be
determined along with tumor to background ratio and these will be summarized
descriptively. Positive and negative lesions by the two imaging techniques will be
cross tabulated overall and by localization area on a lesion level and a patient level.
Agreement calculations will be performed on a patient level and tests of association
may be performed where appropriate.
Preliminary explorations of ⁶⁸ Ga-PSMA-R2 imaging performance relative to
cytology and/or historiathology findings from archival and/or recent bionsy
specimens will be performed for patients with bionsy data available
speemens will be performed for putents will blopsy dua dvalable.

STUDY PROCEDURES AND ASSESSMENTS

	Screening (Day -14 to Day -1 (+1 day)	Imaging Day 1 (+1 day)	Safety Follow-up Day 7 (+1 day)	Safety Follow-up Day 28 (+1 day)
Informed consent	X			
Inclusion/Exclusion Criteria Assessment	X			
Medical History & Demographics	Х			
ECOG Performance Status	X	Х	X	Х
Standard 12-lead ECG	X	Xª		
Disease Assessment: Imaging (CT/MRI or Bone Scan)	X ^b			
Vital Signs: Temperature (Temp), Blood Pressure (BP), Heart Rate (HR), and Respiratory Rate (RR) ^c	Х	Х	Х	Х
PSA	X			
Lab Analysis: Hematology, Blood Chemistry ^d	X	Х	Х	Х
Urine Analysis (Dipstick) ^e	X	Х	X	Х
⁶⁸ Ga-PSMA-R2 Administration		Х		
⁶⁸ Ga-PSMA-R2 PET/CT (Dosimetry) ^f		Х		
PK and Dosimetry Sample Collection (Blood) ^g		Х		
PK and Dosimetry Sample Collection (Urine) ^h		Х		
Adverse Event Collection	X	Х	X	Х
Concomitant Medications	X	X	X	Х

Table 1 Schedule of Procedures and Assessments

^a On Day 1, 12-Lead ECG will be collected after dosage administration.

^bAll patients are required to undergo a CT/MRI and bone scan if indicated (can be performed ≤ 2 months prior to study entry).

^c On Day 1 vital signs (temp, BP, HR, and RR) will be performed before and after to ⁶⁸Ga-PSMA-R2 injection and also at the end of ⁶⁸Ga-PSMA-R2 PET/CT scan.

^d Peripheral venous blood samples will be collected at each visit. On Day 1, blood samples will be collected after administration of ⁶⁸Ga-PSMA-R2.

^e A urine sample will be collected at each visit and analyzed at the clinical site if dipstick results are abnormal. Sample collection on Day 1 will be performed after the administration of IP

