6.3. Administration/ Imaging Period (Day 1)

Eligible patients who have met all inclusion criteria and none of the exclusion criteria will receive an injection of 3 MBq/Kg, but not less than 150 MBq and no more than 250 MBq of ⁶⁸Ga-PSMA-R2. Patient will enter the trial unit on the morning of the exam. Each subject will be allocated one single imaging kit.

- All concomitant medications including PCa therapies taken 2 weeks prior to the IP administration date through the end of study will be recorded.
- Any AEs occurring after the ICF signature will be recorded and followed until resolution.
- Vital signs will be assessed before and after the ⁶⁸Ga-PSMA-R2 injection and at the end of the PET/CT exam.
- ECOG performance status will be assessed.
- Patient will be injected intravenously one single bolus dose of ⁶⁸Ga-PSMA-R2.
- ECG (12-lead) will be recorded immediately after IP administration.

- For patients entering in Phase 1: PET/CT scans will be performed at approximately 20-30 minutes and at 1, 2, 3-4 hours post-injection.
- Patients in the Phase 1 portion of the study will undergo distribution/ dosimetry analysis
- For patients entering Phase 2, patients will have PET/CT imaging reduced to up to 2 whole body scans within the optimal time frame, to confirm the high tumor to background ratio, and agreement compared to standard conventional method.
- Samples for hematology, biochemistry and urinalysis will be collected after the administration of IP.
- Patients entering Phase 1 only: PK and dosimetry blood samples will be collected immediately prior to IP administration, approximately 5, 10, 20, 40 minutes, as well as immediately after, 1, 2, 4, and 6 hours post IP administration.
- Patients entering Phase 1 only: Urine sample for PK will be collected Pre-injection, approximately 0-20 minutes after IP administration, 0-1 hour, 1-2 hours, 2-4 hours, 4-6 hours post-injection.

6.4. Safety Follow-up Visits (Day 7 ± 2 Days and Day 28 ± 3 Days)

After IP administration, two safety follow-up visits will be performed on Day 7 (\pm 2 Days) and Day 28 (\pm 3 Days).

- All concomitant medications including PCa therapies taken 2 weeks prior to IP administration date through the end of study will be recorded.
- Any AEs occurring after the ICF signature will be recorded and followed until resolution.
- ECOG performance status is assessed.
- Vital signs will be assessed.
- Blood samples for hematology, biochemistry and urinalysis will be obtained.

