6.5.3. Clinical Laboratory Assessments

Clinical laboratory assessments for safety monitoring will be performed by an accredited local laboratory. Blood and urine samples for hematology, serum chemistry and urinalysis, will be prepared using standard procedures.

PSA sample will be collected at Screening (unless performed within one month of enrollment and results are available), and results will be entered into the eCRF.

The following laboratory tests will be performed at Screening, Day 1 (after the administration of the IP), Day 7, and Day 28:

- Hematology: White blood cell (WBC) count with differential, red blood cell (RBC) count, Hb, hematocrit, platelet count, mean corpuscular volume (MCV).
- Blood chemistry profile: albumin, alkaline phosphatase (AP), alanine transaminase (ALAT), aspartate transaminase (ASAT), blood urea nitrogen (BUN), corrected calcium, chloride, creatinine, eGFR (preferably CKD-EPI), glucose, uric acid, gamma-glutamyl transpeptidase (GGT), lactate dehydrogenase (LDH), potassium, sodium, total bilirubin and total protein.
- Urinalysis: (dipstick), appearance, color, pH, specific gravity, protein, glucose and occult blood, RBC and WBC counts, Casts per low power field (Casts/lpf), Protein (dipstick test accepted).

Table 2 summarizes general laboratory assessments to be performed.

Hematology	Blood Chemistry	Urinalysis [*]
• WBC with differential	• BUN	• Appearance
• RBC	• Serum creatinine	• Color
• Platelets	• eGFR	• pH
• Hb	• Albumin	• Specific gravity
• MCV	• Total bilirubin	• Glucose
• Hematocrit	• AP	• Occult blood
• PSA (Screening visit only)	• AST/ASAT	• RBC/hpf
	• ALT/ALAT	• WBC/hpf
	• Gamma-GT	• Casts/lpf
	• Sodium	• Protein (dipstick test accepted)
	• Potassium	
	• Chloride	
	• LDH	
	Corrected Calcium	
	• Glucose	
	• Total protein	
	• Uric acid	

 Table 2
 Summary of Laboratory Assessments

*A urine sample will be collected at each visit and analyzed at the clinical site if dipstick results are abnormal. WBC = white blood cell; RBC = red blood cell; Hb = hemoglobin; MCV = mean corpuscular volume; PSA = prostate specific antigen; BUN = blood urea nitrogen; eGFR = estimated glomerular filtration rate; AST/ASAT = aspartate aminotransferase; ALT/ALAT = alanine aminotransferase; gamma-GT = gamma glutamyl transferase; LDH = lactate dehydrogenase; pH = potential of hydrogen; hpf = high power field; lpf = low power field.

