6.5.5.1. Standard 12-Lead ECG

ECGs will be recorded at the screening visit and at Day 1 (after the administration of the IP) to measure the different ECG intervals (RR, PR, QRS, and a more extended QT evaluation according to ICH E14, and heart rate, HR). A single ECG will be taken supine, after 5 minutes rest, and not immediately after a meal. The parameters will be measured as a mean value of minimally 3 beats. The Investigator will note in the electronic CRF (eCRF) whether the ECG is normal or abnormal, as well as the clinical relevance of abnormal ECGs. Clinically relevant abnormalities will be recorded on the AE page of the eCRF.

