6.3. BASELINE

Unless otherwise specified, baseline is defined as the last non-missing measurement taken prior to reference start date (including unscheduled assessments). In the case where the last non-missing measurement and the reference start date and time coincide, that measurement will be considered pre-baseline, but Adverse Events (AEs) and medications commencing on the reference start date will be considered post-baseline.

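### SAP Appendix 1 names the Day 1 visit 'Baseline', although every scheduled Day 1 ECG, laboratory and urinalysis sample is taken after injection

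*SAP*

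**What the plan says.** **The label.** SAP Appendix 1, under the presentation of visits, states: "For outputs, visits will be represented as follows and in that order". The list is Screening, then "Baseline (Day 1", then Day 7 and Day 28. These are the long (default) names; the short name for Day 1 is D1.

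**The baseline rule.** SAP 6.3 says that, unless specified otherwise, "baseline is defined as the last non-missing measurement taken prior to reference start date", counting unscheduled assessments. Protocol 8.2 likewise takes the last non-missing value before administration.

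**The sampling times.**
- ECG: Table 1 footnote a says "On Day 1, 12-Lead ECG will be collected after dosage administration". Protocol 6.3 says "ECG (12-lead) will be recorded immediately after IP administration". Protocol 6.5.5.1 gives the whole ECG schedule: "ECGs will be recorded at the screening visit and at Day 1 (after the administration of the IP".
- Hematology and chemistry: Table 1 footnote d says "On Day 1, blood samples will be collected after administration of" the product. Protocol 6.5.3 says "The following laboratory tests will be performed at Screening, Day 1 (after the administration of the IP), Day 7, and Day 28".
- Urinalysis: Table 1 footnote e and Protocol 6.3 also place the Day 1 sample after injection.
- Vital signs: Table 1 footnote c and Protocol 6.3 schedule Day 1 readings before injection, after injection and at the end of the scan.

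**The concern.** Absolute values and changes from baseline in laboratory parameters and ECG are primary endpoints (Protocol 2.2.1, SAP 14). SAP 6.4 presents by-visit data at the nominal visit, so post-injection Day 1 values fall under the Day 1 name. SAP 14.2 and 14.3 order by-visit summaries of change from baseline and box plots over time for these parameters.

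Under the Appendix 1 name, those outputs would carry a heading containing the word Baseline over values that neither definition admits as baseline. A reader could take the first values after the product was given as pre-product values, and could not make sense of a non-zero change from baseline in a row called Baseline. ECG is the sharpest case, because Day 1 is its only scheduled post-injection record.

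A secondary risk is that the label influences the programming.

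**Working it through.** No figure in the plan is at issue, so there is none to reproduce. The check sets the label against the schedule and counts scheduled time points.

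**Step 1: scheduled time points** (Protocol Table 1 with footnotes, 6.3, 6.4, 6.5.3, 6.5.5.1)

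| Parameter | Before injection | After injection |
|---|---|---|
| ECG | Screening (1) | Day 1 (1) |
| Hematology, chemistry, urinalysis | Screening (1) | Day 1, Day 7, Day 28 (3) |
| Vital signs | Screening; Day 1 pre-injection (2) | Day 1 post-injection; Day 1 end of scan; Day 7; Day 28 (4) |

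**Step 2: apply SAP 6.3 and Protocol 8.2.** For ECG, laboratory and urinalysis data the only scheduled value that qualifies as baseline is Screening. An unscheduled pre-dose value would replace it if one exists. Scheduled post-baseline time points are then 1 for ECG and 3 for laboratory and urinalysis data.

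**Step 3: apply the Appendix 1 name to the display.** The Day 1 row holds post-injection values. Write S for the Screening value and S + d for the Day 1 value. The row headed Baseline then shows a change of (S + d) − S = d, which is zero only if nothing changed.

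**Step 4: what would follow if Day 1 were used as baseline** (conditional, not the planned derivation)
- ECG: no scheduled record follows Day 1, so post-baseline time points fall from 1 to 0. The change-from-baseline summary and the QT/QTc categories of more than 30 and more than 60 msec would have no scheduled data.
- Laboratory and urinalysis: post-baseline visits fall from 3 to 2 (Day 7 and Day 28). For a quantitative parameter, a shift d present on Day 1 and persisting to Day 7 would be reported as (S + d) − (S + d) = 0 instead of d.

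**Step 5: could Step 4 happen?** SAP 6.2 defines the reference start date as a day. SAP 6.3 then adds a tie rule: a measurement whose timing coincides with the reference start date and time counts as pre-baseline. If sample times are missing or unused and the tie is judged by date, a post-injection Day 1 value could be classed as pre-dose and, being the latest such value, become baseline. The Appendix 1 name would reinforce that reading.

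**Step 6: can any Day 1 sample justify the label?** Phase 1 patients give pre-injection blood and urine on Day 1, but those are PK and dosimetry samples (Table 1 footnotes g and h), not safety laboratory tests. Among the primary-endpoint parameters, only vital signs have a scheduled pre-injection Day 1 value, and there the single name covers readings from before and after injection.

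**The case against.** The strongest reply is that Appendix 1 defines no baseline value. It is a set of programming conventions alongside fonts, margins and spelling, and the visit list only supplies display names. Derivation is set in SAP 6.3 and 6.7, and Protocol 8.2 agrees with it. The 6.3 proviso allowing other specifications does not help the label, since a visit name specifies no baseline.

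A reader might infer something stronger: that the SAP holds two competing baseline rules, that change will be calculated from Day 1, and that ECG will have no post-baseline data. The documents do not support this. SAP 14.3 and 14.3.1 order ECG change from baseline, post-baseline markedly abnormal values and QT/QTc increases. With ECGs only at Screening and Day 1, scheduled data can fill those outputs only if Day 1 is post-baseline. A programmer who used Day 1 as baseline would get empty ECG change tables and would probably notice.

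Two further points stand. The name is a default, with a neutral short form available. SAP 8 also says that the templates supplied with the plan describe the format and content of the outputs; these are not in the documents and may already show a separate Baseline row or use D1. In addition, the analysis is descriptive, with no formal testing (SAP 6.6).

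These points limit the consequence but do not remove the contradiction. Nothing in the SAP text corrects the name, and as the stated default it puts post-injection primary safety data under the wrong heading.

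**Conclusion.** The point holds as a presentation error. The Appendix 1 name for Day 1 contradicts the sampling schedule, SAP 6.3 and Protocol 8.2 for ECG, hematology, chemistry and urinalysis. Followed as written, it mislabels the single scheduled post-injection ECG and the first of three post-injection laboratory and urinalysis visits for every dosed patient, up to the 30 planned.

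The derivation is not wrong as specified: baseline is Screening or an unscheduled pre-dose value. Losing the one post-baseline ECG time point, or one of three laboratory visits, is a modest risk. It depends on a programmer following the label or settling the 6.3 tie rule by date alone.

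The conclusion assumes that the templates keep the default name. The counts assume samples taken as scheduled, with no unscheduled records. The change should be made because it concerns primary safety displays and costs almost nothing.

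**What to change.** - In Appendix 1, rename the visit 'Day 1 (post-injection)' for ECG, laboratory and urinalysis outputs, and show a separate 'Baseline' row derived under 6.3.
- For vital signs, show Day 1 pre-injection, post-injection and end-of-scan values separately.
- In SAP 6.3, 14.2 and 14.3, state that scheduled Day 1 ECG, laboratory and urinalysis values are always post-baseline, whether or not a sample time is recorded.
- Check the templates for the same label.

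The cost is a label change in the appendix and templates, extra Day 1 rows for vital signs, and a sentence in each of three SAP sections. No new data are needed.
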